### 5.4 Subject Compliance Monitoring

No compliance monitoring shall be required for this trial, it is expected that each subject shall participate for approximately 1 – 2 hours with no further follow-up required.

### 5.5 Prior and Concomitant Therapy

There are no restrictions regarding medication(s) and/or treatments before and/or after the trial.

### **5.6 Packaging, Receiving, Storage, Dispensing and Return**

The devices will be shipped to the investigator in standard packaging and standard storage procedures shall be employed. The devices will be kept in a secured area.

At the completion of the study, all devices will be returned to the sponsor.

## **6 Study Procedures**

The study procedure shall be broken down into several phases, as described below:

### 1. Phase 1 – Subject enrollment

- Subjects shall be enrolled based on the plan presented previously in the protocol. Informed consent will be required from each subject.
- General demographic data information (age, gender, race, ethnicity, height, weight, comorbidities) will be collected for each subject.

### 2. Phase 2 – Initial Spirometry measurements

- After subject enrollment, the subject will be fitted with both an AffloVest product and Monarch vest
- An initial spirometry baseline will be taken using standard spirometry equipment and according to standard spirometry procedures, without any device on the subject.
- Depending on the subject enrollment number, the appropriate product will be placed onto the subject.
- The device will be turned on to the maximum frequency and intensity settings.
- The subject will be allowed five (5) minutes to acclimate to the device.
- The spirometry measurements will then be repeated in the same manner as above
- The device will be turned OFF and removed, and the subject will be allowed fifteen (15) minutes recovery
- An interim spirometry baseline will be taken using standard spirometry equipment and according to standard spirometry procedures, without any device on the subject.
- Depending on the subject enrollment number, the second appropriate product will be placed onto the subject.
- The device will be turned on to the maximum frequency and intensity settings.
- The subject will be allowed five (5) minutes to acclimate to the device.
- The spirometry measurements will then be repeated in the same manner as above
- The device will be turned OFF and removed, and the subject will be allowed fifteen (15) minutes recovery
- A final spirometry baseline will be taken using standard spirometry equipment and according to standard spirometry procedures, without any device on the subject

### 3. Phase 3 – Survey

- The subject will be provided a brief survey to complete

No interim analysis shall be completed.

## **7 Statistical Procedures**

### **7.1 Sample Size Determination**

This is a pilot investigational trial. No statistical analysis was performed in the generation of the sample size, however similar studies for these types of devices were reviewed to determine an adequate sample size.

### **7.2 Statistical Methods**

The metrics for the study shall be calculated as follows:

- Subject baseline values: An average of the pre-baseline, interim-baseline and post-baseline measurements shall be taken for FEV1, FVC, PEF, FEF25-75% and TV for each subject
- Comparison of the subject baseline values will be made with their values while using each device. A Student's t-test will be used to look for statistically significant differences at the 95% confidence level

Any deviation(s) from the original statistical plan shall be communicated to the IRB and the protocol shall be revised, if required.

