## STUDY SUMMARY

Title	AffloVest Comparative Study for Air Flow in the Lungs
Protocol Number	2018-02
Phase	Device, Phase I
Methodology	
The study will be broken into one (1) arm:
 
 
- AffloVest® & Monarch™
 
 
Within each arm, the order of products will be also randomized.
 
Baseline spirometry (FEV1, FVC, PEF, FEF25-75% and TV) will be taken at the beginning, middle and end of each subject trial without any device on the subject.
 
A product (AffloVest or Monarch vest) will be placed onto subject and turned ON to the highest frequency and intensity settings, then the subject will be given a certain period. The spirometry measurements will then be repeated. The product will be removed and the subject allowed a recovery period, then the other product will be placed on the subject, turned ON and spirometry measurements repeated. A short questionnaire will also be included.

Study Duration	Approximately one (1) month
Study Center(s)	Pulmonary Disease Specialists, PA (d/b/a PDS Research) [name]
Objectives	Investigate impact of high-frequency chest wall oscillation therapy on spirometry values (FEV1, FVC, PEF, FEF25-75% and TV) during use of different products and comparing to baseline values to determine any significant variation in air flow in the lungs.
Number of subjects	10
Main Inclusion and Exclusion Criteria	
Inclusion: Healthy subject, ages 18 – 50
 
Exclusion: Non-ambulatory, diagnosed neuromuscular disorder, currently using any type of oscillation vest therapy, diagnosed co-morbid condition (i.e. lung cancer, other lung disorder or disease), currently enrolled in a medical research study, non-English speaking, presence of the following active implantable devices: pacemakers, neurostimulators, infusion pumps, circulatory support devices, implantable cardioverter defibrillators (ICD's), cochlear implants, presence of head and/or neck injury that has not yet been stabilized, presence of active hemorrhage with hemodynamic instability

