### 1.1 Background

High Frequency Chest Wall Oscillation (HFCWO) is a therapy that has been proven to be effective for many years and is used for airway clearance for patients that have difficulty mobilizing secretions in the lungs. One method to accomplish HFCWO therapy utilizes air bladder compression of the torso to create oscillation in the lungs. Air bladder companies claim “The assumption is that the effectiveness of the treatment can be measured in the mouth airflow which is believed to be the indicator of the efficacy of the therapy”. Air bladder devices claim that they create air shearing forces in the lungs by increasing air flow in the lungs by shaking and compressing the entire torso to supposedly generate airflow in the lungs to mobilize secretions. Moreover, air bladder companies have claimed that they create more air flow in the lungs than the newer oscillation technology. The purpose of this study is to measure and compare airflow actually in the lungs while using two different motorized oscillation HFCWO technologies to determine the actual air flow in the lungs. Lung airflow will be measured using standard pulmonary spirometry clinical equipment. The results will be collected and analyzed.

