## **3 Study Design**

### **3.1 General Design**

This pilot study has been designed as follows:

- One (1) arm
- This is a pilot investigational study, based on the study design there are no blinding or randomization measures taken. It is expected that the degree of bias shall be low based on the subjective endpoints under study. Each subject shall serve as their own control as

baseline spirometry measurements will be performed at the beginning and end of the visit.

- Each subject will participate for a period of approximately two (2) hours.
- There is no subject follow-up, all measurements will be performed within the initial subject visit. At the end of the visit, each subject shall be required to complete a brief survey regarding their experience.

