### **3.2 Primary/Secondary Endpoints**

The following primary and secondary endpoints are to be analyzed in the study:

Primary endpoints:

1. Difference in spirometry measurements (FEV1, FVC, PEF, FEF25-75% and TV) between the AffloVest device and Monarch devices.

Secondary endpoints:

1. Survey results using a Likert scale related to:
  - a. Subject opinion on using each device on a daily basis
  - b. Subject opinion on lifestyle fit for each device
  - c. Subject opinion on lifestyle obtrusiveness of each device
  - d. Subject opinion on mobility during use of each device
  - e. Subject opinion on noise level of each device
  - f. Subject opinion on compliance with treatment of each device

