### 5.3 Method for Assigning Subjects to Treatment/Dosing Groups

Subjects shall be assigned according to the following in order of study enrollment. This approach shall control for any effect from which device is used first by alternating the device order.

Subject Number	First Device	Second Device
1	AffloVest	Monarch
2	Monarch	AffloVest
3	AffloVest	Monarch
4	Monarch	AffloVest
5	AffloVest	Monarch
6	Monarch	AffloVest
7	AffloVest	Monarch
8	Monarch	AffloVest
9	AffloVest	Monarch
10	Monarch	AffloVest

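### The primary endpoint is the AffloVest–Monarch difference, but Section 7.2 analyses only each device against baseline

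*Combined protocol and SAP*

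**What the plan says.** The combined protocol and SAP describes the target comparison in several places.

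- **Section 3.2** lists one primary endpoint: "Difference in spirometry measurements (FEV1, FVC, PEF, FEF25-75% and TV) between the AffloVest device and Monarch devices".
- **Section 1.1** gives the same aim: "The purpose of this study is to measure and compare airflow actually in the lungs while using two different motorized oscillation HFCWO technologies".
- **Section 5.3** alternates which device comes first, and explains: "This approach shall control for any effect from which device is used first by alternating the device order".
- **The Study Summary objective** is worded against baseline: "comparing to baseline values to determine any significant variation in air flow in the lungs".
- **Section 7.2** has two bullets. The first defines the baseline: "An average of the pre-baseline, interim-baseline and post-baseline measurements shall be taken for FEV1, FVC, PEF, FEF25-75% and TV for each subject". The second reads "Comparison of the subject baseline values will be made with their values while using each device" and continues "A Student's t-test will be used to look for statistically significant differences at the 95% confidence level".

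Section 7.2 does not say whether the t-test is paired. Section 3.1 implies within-subject comparison by saying "Each subject shall serve as their own control as" baseline readings are made during the visit, but that sentence concerns baseline and not the other device. No section specifies an analysis of AffloVest against Monarch.

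**The concern.** The endpoint section asks how the two devices differ. The methods section asks whether each device differs from no device. A team that follows Section 7.2 exactly will finish with two sets of baseline comparisons and nothing on the primary endpoint.

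The likely consequence is that readers set the two baseline results side by side and draw a device conclusion from the pattern. That fails in both directions. If the devices are equal, one can reach significance and the other miss it by chance. If they differ, both can be significant and the difference goes unreported. The protocol does not say it would reason this way, but it offers no other route to a conclusion on its primary endpoint. The study is unblinded and has five measures under one endpoint, so an unspecified contrast also leaves room for choices made after the data are seen.

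**Working it through.** **Step 1: the text.** The endpoint (3.2), the purpose (1.1) and the order allocation (5.3) point to device versus device. The summary objective and Section 7.2 are worded as device versus baseline. The t-test sentence sits in the same bullet as the baseline comparison and directly after it, so that comparison is its natural referent. Section 7.1 states that the sample size rests on no calculation, so there is no figure of the plan's own to reproduce.

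**Step 2: what the data allow.** Let A and M be a subject's readings on AffloVest and Monarch, and B the average of the three baseline readings. Then (A − B) − (M − B) = A − M. The baseline cancels, so the direct contrast is available for every subject who completes both devices. What is missing is its specification.

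**Step 3: can two baseline tests replace the direct test?** From the documents: n = 10, one common baseline averaging three readings, 95% confidence level. Assumed, because the documents are silent: within-subject SD of 1, independent errors, one reading per device, two-sided paired t-tests at 0.05 (9 df). There were 200,000 simulated trials per setting. The standard errors are:

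- device versus baseline: √[(1 + 1/3)/10] = 0.365 SD
- device versus device: √(2/10) = 0.447 SD

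*Equal true effects of both devices:*

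| Common effect (within-subject SD) | Exactly one device significant vs baseline |
|---|---|
| 0 | 9.2% |
| 0.25 | 15.8% |
| 0.5 | 31.7% |
| 0.8 | 43.1% |
| 1.0 | 37.7% |
| 1.25 | 21.9% |
| 1.5 | 8.3% |
| 2.0 | 0.4% |

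The direct paired test rejects in 4.9% to 5.0% at every effect.

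*Unequal true effects:*

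| Effects (SD) | Both devices significant vs baseline | Direct test significant |
|---|---|---|
| 1.5 and 3.0 | 95.4% | 84.6% |
| 2.0 and 3.5 | 99.8% | 85% |

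For the first row, the noncentral t distribution with noncentrality 1.5/0.447 = 3.35 and 9 df also gives 84.6%. In 80% of those trials all three tests are significant: Section 7.2 would report two positive results and omit a detectable difference.

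**Step 4: sensitivity to the error assumption.** Suppose subjects also vary in their response to wearing any device, through a shared on-device component with SD equal to the within-subject SD. Discordance is then 8% at zero effect, 19% at 0.5, 29% at 0.8, 32% at 1.0 and 23% at 1.5. With that SD doubled, the highest value among the effects tried is about 22%. The shared component cancels in A − M, so the direct test is unaffected.

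**Step 5: what the direct analysis would deliver.** The 95% CI half-width is t(0.975, 9 df) × √(2/10) = 2.262 × 0.447 = 1.01 within-subject SD. In SDs of the paired difference it is 2.262/√10 = 0.72. A period term leaves 8 df and gives 2.306/√10 = 0.73. The difference detectable with 80% power is 1.00 SD of the paired difference (1.01 with a period term). None of this can be put in litres or L/min, because no SD is given.

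**The case against.** The strongest reply is that the t-test sentence names no contrast, and that Section 3.2 supplies one. With a common baseline the plan is a single subtraction from its primary endpoint, so the contrast would probably be computed. That lowers the practical risk, but it does not make the analysis pre-specified. Even on this generous reading, the contrast, pairing, handling of period, estimate and interval are all unstated, and a 95% confidence level for significance is not a commitment to report an interval.

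Further points have some force:

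- **Omission or contradiction.** Comparing with baseline and comparing devices are compatible aims, and the summary objective does refer to different products. The core defect is the omission in Section 7.2. The differing emphasis still has to be reconciled, and Section 2 states neither comparison clearly.
- **The 43% figure.** It depends on independent errors and falls when subjects share a response to wearing any device. It is an illustration near the peak, and the textual finding does not rest on it.
- **Pilot status.** This is a 10-subject, single-visit study in healthy volunteers. That explains the absent sample-size calculation. It does not explain a primary endpoint without an analysis in a plan that commits to significance testing.
- **Paired test or period term.** Offering both leaves a choice open. With 5 subjects per sequence the point estimate is the same and the half-widths are 0.72 and 0.73 SD of the paired difference, so the choice matters little, but the text should name one.

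**Conclusion.** The concern holds and must be fixed before analysis. Carried out as written, Section 7.2 leaves the sole primary endpoint without a test, an estimate or an interval, and no other section supplies them. This conclusion comes from the text and needs no numerical assumption.

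The numbers show only why the baseline tests are no substitute. Under the stated assumptions, the chance of a misleading split between two equal devices runs from 0.4% to 43% depending on the true effect, with a lower peak if subjects share an on-device response. A direct test would hold its 5% level throughout.

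**What to change.** Replace the second bullet of Section 7.2 with text such as:

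> *Primary analysis: for each spirometry measure, the within-subject difference AffloVest minus Monarch, both readings taken with the device on, will be analysed by a paired t-test and reported as a mean difference with its 95% CI. Each device will also be compared with the averaged baseline by paired t-test; these comparisons are supportive. A device difference will not be inferred from one device being significant against baseline and the other not.*

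If the sponsor prefers the two-period crossover analysis with a period term, name that instead of the paired t-test, but name only one. It would be sensible to add how the five measures will be read together, since each then carries a primary test.

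Amend the objective in the Study Summary so that the AffloVest–Monarch difference is the primary comparison and the comparison with baseline is supportive. Section 2 can be brought into line at the same time.

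The cost is three sentences in Section 7.2 and one clause in the summary objective, made before analysis. Section 7.2 already provides for protocol revision and communication to the IRB. No new data, visits or subjects are needed.

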Study product, Dose, Route, Regimen	
The International Biophysics AffloVest® and Hill-Rom Monarch™ will be included in the study.
 
Each subject will be properly fitted with a product and then the product will be turned ON. The subject will wear the product for a brief time before taking spirometry readings. The subject will then switch to a different product after a recovery period and the procedure will be repeated. Each subject will then be asked to fill out a short questionnaire.

Duration of subjects participation	One (1) day, approximately two (2) hours per subject

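### Section 7.2 sets ten device-versus-baseline t-tests at 5% each with no multiplicity rule; if the tests are paired, the chance of at least one false positive is roughly 20% to 40%

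*Combined protocol and SAP*

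**What the plan says.** The Summary gives as objective the study of spirometry values during use of the products, "comparing to baseline values to determine any significant variation in air flow in the lungs". It names five measures (FEV1, FVC, PEF, FEF25-75% and TV), two devices and 10 subjects.

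Section 7.2 carries this out in two steps. The baseline is a mean of three readings: "An average of the pre-baseline, interim-baseline and post-baseline measurements shall be taken for FEV1, FVC, PEF, FEF25-75% and TV for each subject". Then: "Comparison of the subject baseline values will be made with their values while using each device". The test and its level follow: "A Student's t-test will be used to look for statistically significant differences at the 95% confidence level".

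Section 7.2 does not say whether the t-test is paired or two-sided. Section 3.1 points to pairing, because it treats each subject as his or her own control. No section names a lead measure, orders the tests, divides alpha or labels these comparisons descriptive. On sample size, 7.1 says: "No statistical analysis was performed in the generation of the sample size".

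The primary endpoint in 3.2 is a different comparison, AffloVest against Monarch on the same five measures. Section 7.2 names no test for it.

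**The concern.** Two devices and five measures give ten tests, each with its own 5% chance of a false positive. The Summary objective singles out no measure or device and does not say how many significant results are needed. Nothing in the plan therefore prevents a single chance result among the ten from being presented as an effect of a vest on lung airflow.

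This matters because Section 1.1 sets the study against competing manufacturers' claims about airflow. Under the paired model below, a chance finding would usually mark one vest and not the other. A reader could easily take that for a difference between products, which these tests do not assess.

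**Working it through.** The documents state no family-wise error rate and no power, so there is no figure to reproduce.

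**Inputs from the documents.** Five measures and two devices (Summary, 7.2); 10 subjects (Summary); baseline as the mean of three readings (7.2); 5% per test (7.2).

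**Assumptions not in the documents.** Two-sided tests; paired tests; normal errors with equal variance with and without a vest; a common correlation r among the five measures, varied over its range.

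1. Number of tests: 5 × 2 = 10.

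2. Reference value if all ten were independent: 1 − 0.95^10 = 40.1%.

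3. Correlation between the two devices' differences. Both subtract the same averaged baseline. With error variance σ² per reading, each difference has variance σ² + σ²/3 = 4σ²/3, and the two share covariance σ²/3. The correlation is (1/3)/(4/3) = 0.25.

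4. Simulation with no device effect (40,000 trials; 10 subjects; paired t-test on 9 degrees of freedom; two-sided 5%):

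| r among measures | Chance of at least one significant result in ten |
|---|---|
| 0 | 39.6% |
| 0.3 | 37.4% |
| 0.5 | 34.1% |
| 0.7 | 28.5% |
| 0.8 | 24.8% |
| 0.9 | 20.2% |

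A separate run of the same size agreed within 0.4 percentage points and gave 9.8% at the limit r = 1. There, only two distinct tests remain.

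5. At r = 0.5, exactly one device is flagged in 30.0 of the 34.1 percentage points.

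6. Unequal correlations. With TV independent and the other four measures correlated at 0.5, 0.7 or 0.9, the chance is 36.0%, 32.4% or 26.7%.

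7. Sensitivity to pairing. With a two-sample t-test, the answer depends on the share of variance that lies between subjects:

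| Between-subject share | r = 0 | r = 0.5 |
|---|---|---|
| 0 | 41.4% | 34.9% |
| 0.5 | 5.1% | 4.7% |
| 0.8 | 0.15% | 0.16% |

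The rate falls because differences between subjects stay in the denominator of the test. For the same reason, a real effect would be harder to detect.

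8. Effect of control. Holm's first step tests the smallest p-value at 0.05/10 = 0.005. The simulated chance of any false positive under Holm is 4.7% at r = 0.5 and at most 5.0% over the range in step 4.

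9. Price of control. By the noncentral t distribution at n = 10 and 80% power, the detectable paired effect is 1.00 SD of the within-subject difference at alpha 0.05, and 1.48 SD at alpha 0.005.

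**The case against.** The strongest reply is that the plan claims less than the concern supposes.

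- **No decision rule.** A reader might infer that the study will declare an effect about one time in three when there is none. The documents do not support that. They contain no success criterion and no rule that one significant result is enough. The Summary wording can be read simply as asking whether variation exists. Section 7.2 attaches its 95% level to each comparison and promises no family-wise level, so the inflated rate does not contradict a stated figure.
- **Unstated inputs.** The one-in-three figure needs paired tests and a correlation near 0.5. Neither is written down. Three of the measures come from the same forced manoeuvre by the protocol's own definitions, so higher correlation among them is plausible. A two-sample test could bring the rate to about 5% or below.
- **Exploratory character.** The Summary calls the study Phase I, 3.1 and 7.1 call it a pilot, and Section 2 speaks only of a potential relationship.
- **Not the primary endpoint.** The ten tests are not the between-device comparison of 3.2.

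The first two points stand as limits on the claim: it must be conditional and given as a range. The third does not remove it, because the pilot label leaves the significance testing in 7.2 in force. The fourth is correct, but these ten comparisons are the only inferential tests that 7.2 specifies, and controlling the between-device comparison would not control them.

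**Conclusion.** The concern holds in conditional form. Ten tests at 5% with no multiplicity rule are a fact of the plan. If they are paired, with equal error variance on and off the vest, the chance of at least one false positive when neither vest has an effect is roughly 20% to 40% for correlations from 0.9 down to 0. At an assumed 0.5 it is about 34%. An isolated significant result is therefore weak evidence of a device effect.

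The size depends on a pairing that 3.1 implies but 7.2 does not state, and on a correlation that the documents do not give. Under a two-sample test it could be far smaller.

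**What to change.** In 7.2, state that the t-tests are paired and two-sided. Then choose one of two routes:

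- **Control.** Apply Holm across the ten device-versus-baseline p-values at an overall two-sided 5%, and claim variation only for the comparisons that survive.
- **Describe.** Report the ten comparisons as mean changes with 95% confidence intervals and no significance claim. Reword the Summary objective so that the aim is to estimate the change from baseline.

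Neither route needs new subjects or measurements. Holm costs sensitivity: the effect detectable at its first step rises from about 1.0 to about 1.5 SD. The descriptive route gives up the only significance tests the plan specifies, so a test of the between-device primary endpoint in 3.2 must then be written into 7.2 separately.
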